## 6.6 Prior and Concomitant Medications

Prior and concomitant medications will be coded with the World Health Organization Drug Dictionary and listed. All concomitant medications taken after first dosing of study drug will be summarized for the Safety Population by dose level, treatment, and overall. All concomitant medications during the Placebo Lead-in Period will be summarized overall. All prior and concomitant medications will be listed.

## 6.7 Exposure and Compliance

Treatment duration within each dose level will be summarized with descriptive statistics for ATR-101 and placebo separately and overall. Treatment duration will be calculated as follows:

$$\textit{Treatment duration in days} = \textit{last dose date} - \textit{first dose date} + 1.$$

If the last dose date is not available within a dose level, the date prior to the first dose date of the next dose level will be used.

The number of tablets administered will be summarized within each dose level with descriptive statistics for ATR-101 and placebo separately and overall.

$$\textit{Number of tablets administered} = \textit{number of tablets dispensed} - \textit{number of tablets returned}$$

Compliance within each dose level and overall will be summarized with descriptive statistics for ATR-101 and placebo separately. The percentage of subjects with compliance <80%, 80-120%, and >120% will also be tabulated.

Dose Levels 1, 2, and 3:

$$\text{Compliance (\%)} = 100 \times \text{number of tablets administered} / (\text{treatment duration} \times 2).$$

Dose Levels 4 and 5:

$$\text{Compliance (\%)} = 100 \times \text{number of tablets administered} / (\text{treatment duration} \times 4).$$

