- ^k Obtained for females of childbearing potential who are not surgically sterile or who have not been naturally postmenopausal for at least 12 consecutive months (i.e., who have had menses any time in the preceding 12 consecutive months). A serum pregnancy test will be performed at Screening. A urine pregnancy test will be performed prior to dosing on Day 1 of each Dose Level and at the Final Study Visit or Early Termination Visit.
- ^l Blood for PK analysis of ATR101 and its metabolites in plasma will be obtained on Day 1 of each Dose Level at pre-dose and 1, 2, 3, and 4 hours post-dose; on Day 15 of each Dose Level at pre-dose and at the Final Study Visit or Early Termination Visit. A window of \pm 10 minutes is permitted around each sampling time-point.
- ^m The first dose will be administered on site on Day 1 and Day 15 of each dose level.
- ⁿ All bottles and unused tablets must be returned to the study site on Day 1 and Day 15 of each dose level and at the Final Study Visit or Early Termination Visit.
- ^o IMP compliance will be assessed by counting the number of tablets returned and determining if the correct number were taken within the window of 80% to 120%.
- ^p AEs will be collected from the time the subject signs the informed consent form until 30 days after the last dose of IMP.
- ^q Tests do not need to be repeated on Day 1 of Baseline Lead-In if the subject's clinical condition has not changed and these tests were done \leq 14 days prior to Day 1

TABLE OF CONTENTS

Synopsis	2
Table Of Contents	8
LIST OF IN-TEXT TABLES	11
LIST OF IN-TEXT FIGURES.....	11
LIST OF APPENDICES.....	12
List of Abbreviations	13
1 Introduction.....	15
1.1 Description of Congenital Adrenal Hyperplasia.....	15
1.2 Rationale for Use of ATR-101 in Congenital Adrenal Hyperplasia.....	16
2 Study Objectives	17
2.1 Primary Objective	17
2.2 Secondary Objectives	17
3 Investigational Plan.....	18
3.1 Overall Study Design and Plan.....	18
3.1.1 Screening Period	20
3.1.2 Baseline Lead-in Period.....	20
3.1.3 Dose Level 1 (ATR-101 125 mg BID and matching placebo).....	20
3.1.4 Dose Levels 2, 3, 4 and 5.....	21
3.1.5 Final Study Visit	21
3.1.6 Follow-up Visit	21
3.2 Rationale for Study Design and Dose Levels	21
3.3 Efficacy Assessment.....	23
3.4 Safety Assessment	23
4 Study Population Selection.....	24
4.1 Study Population.....	24
4.2 Inclusion Criteria	24
4.3 Exclusion Criteria	25
5. Study Treatment.....	26
5.1 Assignment of Subject Identification Numbers.....	26

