5.3 Treatments Administered

The Baseline Lead-in Period will administer placebo tablets for 14 days. The tablets will match the ATR-101 125 mg tablets and be administered BID.

Starting with Dose Level 1, each dose level will consist of a 28 day dosing regimen consisting of 14 days of ATR-101 treatment followed immediately by 14 days of matching placebo washout. Bottles containing 38 tablets will be supplied for each 14 day dosing period which allows for 5 extra days of dosing to accommodate visit windows (see Pharmacy Manual). Table 3 presents the tablets and dosing regimen by Dose Levels.

Table 3 ATR-101 Dose Levels and Tablet Doses.

Dose Level	14 day Treatment Period		14 day Washout Period	
	ATR-101 Tablet Strength Dispensed	ATR-101 Dosing	Placebo Tablet Dispensed	Placebo Dosing
1	125 mg	1 tablet BID	Matching 125 mg tablet	1 tablet BID
2	250 mg	1 tablet BID	matching 250 mg tablet	1 tablet BID
3	500 mg	1 tablet BID	matching 500 mg tablet	1 tablet BID
4	250 mg and 500 mg	1 tablet each BID	matching 250 mg and 500 mg tablets	1 tablet each BID
5	500 mg	2 tablets BID	matching 500 mg tablet	2 tablets BID

Only the doses presented in Table 3 will be permitted. No other doses will be allowed.

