5.3.6 Compliance with IMP

The IMP is to be dispensed by qualified personnel at the study center and only to subjects enrolled in the study. Subject compliance to therapy will be assessed at scheduled study visits by counting the number of tablets returned. Treatment compliance is defined as the subject taking 80% to 120% of the study tablets to be taken during the dosing period for a given dose level. Subjects found to be outside of the definition of compliance may be discontinued from the study at the discretion of the PI or SI.

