6 STUDY PROCEDURES

6.1 Allowable Variation in Study Visits

Visits and the protocol defined days for each specific period/procedure should be adhered to as much as possible. However, there is flexibility to allow for logistical considerations and to accommodate scheduling conflicts. Variations to the protocol defined visit dates (i.e. study days) may be allowed depending upon the specific circumstances.

- Screening Visit. Up to 21 days.
- Baseline Lead-in Period. A minimum of 14 days must be completed but an additional 3 days beyond the 14 day period is allowed.
- Dose Levels 1-5
 - ATR-101 Treatment Period
 - A minimum of 11 days (22 doses) of ATR-101 must be taken prior to drawing blood samples for an assessment of efficacy and safety. Therefore, sample collection cannot occur earlier than the 12th day of dosing for a given dose level.
 - A maximum of + 3 days is allowed beyond the scheduled 14 day ATR-101 treatment period.
 - Placebo Washout Period
 - A minimum of 11 days (22 doses) of placebo must be taken prior to drawing blood samples for an assessment of efficacy and safety. Therefore, sample collection cannot occur earlier than the 12th day of dosing for a given dose level.
 - A maximum of + 3 days is allowed beyond the scheduled 14 day placebo treatment period.
- Follow-up visit. A window of ± 3 days is permitted.

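### SAP 6.7 counts tablets due only up to the subject's own last dose, so a course stopped early scores 100% where Protocol 5.3.6 counts the missed tablets

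*SAP*

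**What the plan says.** Protocol 5.3.6 sets the standard, level by level: "Treatment compliance is defined as the subject taking 80% to 120% of the study tablets to be taken during the dosing period". Footnote o of the Schedule of Assessments applies the same 80% to 120% window to the tablet count. Protocol 5.3 makes each dosing period 14 days, and Protocol 6.1 lets the actual period run from 11 to 17 days.

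SAP 6.7 defines treatment duration as the last dose date minus the first dose date, plus one day. Compliance is 100 times tablets administered, divided by duration times 2 (Dose Levels 1 to 3) or times 4 (Dose Levels 4 and 5), separately for ATR-101 and placebo. It then adopts the protocol's bands: "The percentage of subjects with compliance <80%, 80-120%, and >120% will also be tabulated".

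A different end date is used only when the subject's own is missing: "If the last dose date is not available within a dose level, the date prior to the first dose date of the next dose level" is then substituted. SAP section 7, which lists changes from the planned analysis, does not mention the new denominator.

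**The concern.** The same bands are applied to two different quantities. The protocol asks what share of the tablets due was taken. The SAP asks what share was taken of those due before the subject's last dose. The two agree when dosing runs to the visit and part when it stops early. The SAP figure cannot fall below 100% because of tablets left untaken after the last dose.

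This does not depend on missing or faulty data. Protocol 7.3 has sites confirm the day and time of the last dose and count tablets at each visit, so the SAP formula is applied with all its inputs present.

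Two things are at stake. First, efficacy at each level rests on one Day 15 17-OHP value, and a reader will use the compliance table to judge whether that level was taken as planned. Second, sites may discontinue a subject under the protocol's definition, and extreme noncompliance is a ground for replacement in Stage 1. The study report could then show 100% for a subject removed or replaced for non-compliance.

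**Working it through.** **Inputs**
- Tablets per day: 2 at Dose Levels 1 to 3, 4 at Dose Levels 4 and 5 (Protocol Table 3; SAP 6.7).
- Scheduled period: 14 days (Protocol 5.3).
- Allowed period: at least 11 days (22 doses), at most 14 + 3 = 17 days (Protocol 6.1).
- Compliant band: 80% to 120% (Protocol 5.3.6; SAP 6.7).

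**Check of the plan's own counts.** Protocol 5.3 states "Bottles containing 38 tablets will be supplied for each 14 day dosing period which allows for 5 extra days of dosing": 14 × 2 + 5 × 2 = 38, which agrees. Protocol 6.1 gives 11 days as 22 doses: 11 × 2 = 22, which agrees. Tablets due in a scheduled period are therefore 28 at 2 a day and 56 at 4 a day. The documents give no worked compliance figure to reproduce.

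**Formulas.** Let a subject take every tablet, k a day, through day d and then stop. Let v be the number of dosing days before the end-of-period visit.
- SAP: 100 × kd / (kd) = 100% for every d.
- Tablets due to the visit: 100 × kd / (kv) = 100 × d/v.

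The tablet count k cancels, so the result is the same at all dose levels.

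**Results at 2 tablets a day**

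| Last day dosed | Tablets | SAP 6.7 | v = 11 (22 due) | v = 14 (28 due) | v = 17 (34 due) |
|---|---|---|---|---|---|
| 8 | 16 | 100% | 72.7% | 57.1% | 47.1% |
| 9 | 18 | 100% | 81.8% | 64.3% | 52.9% |
| 11 | 22 | 100% | 100% | 78.6% | 64.7% |
| 12 | 24 | 100% | – | 85.7% | 70.6% |
| 13 | 26 | 100% | – | 92.9% | 76.5% |
| 14 | 28 | 100% | – | 100% | 82.4% |

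**Where the band changes.** The 80% line is 0.8v: 8.8 days, 11.2 days and 13.6 days. The SAP band is wrong for stops up to day 8, day 11 and day 13 respectively.

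**Stops that still satisfy the 11-day minimum.** Among stops on day 11 or later, the band changes for none at v = 11, for day 11 only at v = 14, and for days 11, 12 and 13 at v = 17.

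**What the SAP formula does detect.** If 14 of 28 tablets are missed at scattered times but the last dose is on day 14, the SAP gives 14/28 = 50%. Only the tail after the last dose is lost.

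**The case against.** The case on the other side is substantial, and most of it stands as a limit on the point.

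- **Nothing inferential uses the percentage.** Responders are tabulated on the Safety Population (SAP 6.8). Per Protocol entry depends on at least 11 days of ATR-101 at Dose Level 1, a 17-OHP assessment and significant deviations (SAP 6.3.3). Sites act on the protocol's tablet count. This stands.
- **A short course is visible elsewhere.** SAP 6.7 also summarises duration and tablets administered by dose level, separately for ATR-101 and placebo. A day-8 stop enters those as 8 days and 16 tablets, which would be conspicuous among 9 to 17 subjects. This stands, but it does not correct the subject's compliance band.
- **Early stops should not yield a Day 15 reading.** Protocol 6.1 says that 11 days of ATR-101 "must be taken prior to drawing blood samples for an assessment of efficacy and safety". A stop before day 11 with a Day 15 sample would also be a deviation, to be recorded under Protocol 10.8. This stands: it makes such cases less likely, not impossible.
- **Dividing by days on drug is defensible.** It separates adherence while treated from length of treatment, and Protocol 5.3.5 allows dosing to be withheld for medical reasons. As a separate measure that is reasonable. It is not the protocol's measure, yet it is reported against the protocol's bands.

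A reader might infer that every stop by day 11 is misclassified. That holds only for an interval of exactly 14 days. A reader might also infer that the formula reflects subjects choosing to stop. The documents do not say so; a stop may have any cause, including a directed one.

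**Conclusion.** The SAP formula contradicts the protocol definition whose bands it borrows, and it gives some subjects the wrong band with complete data. For a subject who takes every tablet and then stops, it reports 100% against d/v by tablets due. A day-8 stop is overstated by 27, 43 or 53 percentage points at 11, 14 or 17 days (100 minus 73, 57 or 47).

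These figures assume full dosing until the stop, a recorded last dose date, and tablets due up to the evening before the actual visit. Protocol 6.11 supports the last assumption, since a subject whose visit is rescheduled keeps dosing until then. The number of subjects affected cannot be known from the documents.

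The consequence is limited to one descriptive table. A reader might go further and infer that the primary result is compromised, or that a Day 15 non-response could not be told apart from untaken drug. The documents do not support this: the responder analysis is independent of the percentage, the companion summaries show short courses, and Protocol 6.1 restricts the efficacy draw. Nor do they give a time course for 17-OHP recovery after the last dose, so the effect of a late gap on the Day 15 value cannot be sized.

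**What to change.** In SAP 6.7, define compliance as 100 × tablets administered / tablets due, where tablets due is the number of days from the first dose of the period to the day before the first dose of the next, times 2 or 4.

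- ATR-101 period: ends the day before the actual Day 15 visit.
- Placebo period: ends the day before the next Day 1 or the Final Study Visit.
- No following dose because of early termination: end at the Early Termination Visit or the documented discontinuation date, and state which applies.
- Medically directed interruptions or stops: flag and report separately, so that they are not read as non-adherence.
- Keep last dose minus first dose plus one for treatment duration only.
- Record the denominator in SAP section 7 if any difference from Protocol 5.3.6 is kept.

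A fixed 28-tablet denominator would not do. It would put fully adherent subjects outside the band at both ends of the allowed window: 22/28 = 78.6% at 11 days and 34/28 = 121.4% at 17 days.

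The cost is SAP wording and one derived variable, from dates the visits already collect. No clinical procedure changes. Reported compliance may be slightly lower.

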## 6.8 Primary Efficacy Analyses

The percentage of responders will be tabulated for the Safety Population overall. A responder is defined as a subject who meets the primary outcome measure of Day 15 17-OHP  $\leq 2 \times \text{ULN}$  (ULN adjusted as needed for the menstrual cycle phase of subjects who are premenopausal women) at any dose level.

The percentage of subjects showing “drug effect” will be tabulated for the Safety Population overall. A subject showing “drug effect” is defined as a subject who is a responder or who has a negative mean percentage change in 17-OHP from Day 1 to Day 15 for Dose Levels 1-5.

The percentage of responders and percentage of subjects showing “drug effect” will also be tabulated for the Per Protocol Population overall as a sensitivity analysis to test the robustness of the primary result.

The change and percentage change in 17-OHP will also be calculated from Day 15 to Day 1 of the next dose level as follows:

- Change and percentage change from Dose Level 1 Day 15 to *Dose Level 2 Day 1*
- Change and percentage change from Dose Level 2 Day 15 to *Dose Level 3 Day 1*
- Change and percentage change from Dose Level 3 Day 15 to *Dose Level 4 Day 1*
- Change and percentage change from Dose Level 4 Day 15 to *Dose Level 5 Day 1*
- Change and percentage change from Dose Level 5 Day 15 to *Final Study Visit (Visit Day 29)*

The percentage of placebo responders will be tabulated for the Safety Population overall. A placebo responder is defined as a subject who meets Day 1/Final Study Visit 17-OHP  $\leq 2 \times \text{ULN}$  at any dose level, i.e. the 17-OHP at the italicized visit above is  $\leq 2 \times \text{ULN}$ .

The percentage of subjects showing “placebo effect” will be tabulated for the Safety Population overall. A subject showing “placebo effect” is defined as a subject who is a placebo responder or who has a negative mean percentage change in 17-OHP from Day 15 to Day 1 of the next dose level.

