3.1.5 Final Study Visit

The Final Study Visit will take place once a subject has met the primary outcome measure at the completion of Dose Levels 1-4 or at the completion of Dose Level 5. This visit will be the final visit to the study center.

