3.2 Rationale for Study Design and Dose Levels

CAH is a rare disease with a limited number of potential subjects. Therefore, the study design must derive as much information as possible from each subject while simultaneously presenting as little risk as possible. This study protocol provides the potential for each subject to achieve the primary outcome measure at the lowest possible dose with a minimum duration of exposure (i.e. 14 days per dose level). In addition, the placebo Washout Period

ensures that each subject has returned to baseline status prior to receiving the next highest dose of ATR-101. This period also serves to verify that changes in adrenal steroids and steroid intermediates are due to ATR-101 effects. Thus, this protocol design will generate a robust dataset with a limited number of subjects which can establish proof of concept for the use of ATR-101 in CAH.

The starting dose for all subjects will be ATR-101 125 mg taken BID orally with food. This dose corresponds to approximately 3 mg/kg/day for a 75 kg individual and is intended to be a non-effective dose. While the 3 mg/kg/day dose was efficacious in dog studies, the exposures (i.e. $AUC_{0-24 \text{ hr}}$ mean $\sim 4700 \text{ ng}\cdot\text{hr}/\text{mL}$) were much higher relative to the projected corresponding exposures in humans. Based on pharmacokinetic modeling from the available human data (ACC subjects and healthy volunteer food effect study¹³), the 125 mg BID dose will provide a steady-state $AUC_{0-24 \text{ hr}}$ of $\sim 2308 \text{ ng}\cdot\text{hr}/\text{mL}$. Dose Level 2 (250 mg BID) will provide an $AUC_{0-24 \text{ hr}}$ of $\sim 4616 \text{ ng}\cdot\text{hr}/\text{mL}$. Each subsequent dose level (3, 4 and 5) will increase the ATR-101 dose by 500 mg per day, with projected steady-state $AUC_{0-24 \text{ hr}}$ values of ~ 9234 , 13850 and $18467 \text{ ng}\cdot\text{hr}/\text{mL}$, respectively. Thus, the projected exposures span a non-effective range up to approximately 4-times the effective exposure observed in the dog studies which allows for potential pharmacokinetic/pharmacodynamic differences between dogs and humans.

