5.3.9 Glucocorticoid and Mineralocorticoid Replacement for CAH

Subjects must continue to receive GC and MC according to individual regimens established prior to entering the study. The regimen should remain as stable and unchanged as possible to minimize potential confounding effects on efficacy outcome measures. However, changes are permitted to ensure subject safety. It is not expected that ATR-101 will have a direct effect on GC replacement therapy as the GC synthetic pathway is already compromised in CAH. Therefore, decreasing cortisol precursors (i.e. 17-OHP) should have no effect on glucocorticoid requirements over the 14 day ATR-101 treatment period.

The timing of glucocorticoid replacement therapy may have an impact on the measurement of 17-OHP. Replacement steroids (GC and MC) must not be taken on the mornings when adrenal steroids/steroid intermediates are being assessed (i.e. Day 15) as this could confound efficacy endpoint measures. GC and MC replacement doses may be given after blood samples are obtained for laboratory assessments.

Approximately 75% of CAH subjects have deficiency in the mineralocorticoid pathway in addition to the GC pathway.⁵ Thus, the majority of subjects in this study are anticipated to be on MC replacement. ATR-101 inhibition of the MC pathway for these subjects should not have an effect on MC replacement therapy. Subjects that enter the study with sufficiently intact endogenous MC production may be impacted by suppression of this pathway by ATR-101. However, pharmacological doses of GC, especially shorter acting ones such as hydrocortisone, also confer MC activity and the need for replacement MC is not usually required.¹⁴

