6.11 Timing of Pharmacodynamic Blood Samples and Dosing of Replacement Steroids

Adrenal steroids and steroid intermediates have a diurnal rhythmicity with peak 17-OHP occurring at around 8:00 AM. Thus, it is extremely critical that the timing of sample collection for efficacy endpoints and dosing of replacement steroids be precise and consistent. Every attempt should be made to collect the sample between 8:00-9:00 AM, but no later than 10:00AM. Study visits that require blood sample collection for steroid hormones, must adhere to the following:

- Morning dose of replacement GC and MC must not be given until after the blood sample is collected
- Blood sample collection must be done prior to **10:00 AM**

If both of these conditions are not met, the blood sample for steroid hormones must not be collected; the visit procedures should not be performed and the study visit must be rescheduled for the next day or as soon as feasible. The subject should continue taking study drug with the last dose occurring the evening prior to the rescheduled visit.

Dosing of GC and MC may take place after collection of blood samples for adrenal steroids and steroid intermediates.

Approximately 20 mL of blood will be collected for steroid hormone testing and approximately 10 mL of blood will be collected for testing synthetic glucocorticoid levels. If exogenous GC levels are suspected of confounding the efficacy outcome measures, additional testing may be performed. Further details on sample collection and handling are provided in the Laboratory Manual.

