7.6 Final Study Visit

The Final Study Visit will take place if the primary outcome measure is met (17-OHP ≤ 2 x ULN) or at the completion of Dose Level 5. The following procedures will be performed.

- Confirm that the morning dose of replacement steroids (GC/MC) was not taken or if taken confirm the day and time of the last dose
Note: If the morning dose of replacement steroids (GC/MC) was taken, it is acceptable to complete the Final Study Visit
- Confirm the day and time of the last dose of IMP
- Perform drug accountability and confirm compliance with IMP
- Review of concomitant medication
- Assess AEs
- Complete physical examination
- Vital signs (including blood pressure, pulse, respiration, body weight and temperature)
- 12-lead ECG
- Blood sampling for hematology, serum chemistry, PT/aPTT/INR
- Urinalysis
- Urine pregnancy testing (β -hCG) for females who are not surgically sterile or who have not been naturally postmenopausal for at least 12 consecutive months (i.e., who have had menses any time in the preceding 12 consecutive months)
- **Blood sampling for steroids/steroid intermediates (before 10 AM)**
- Blood sampling for exogenous glucocorticoid levels
- Blood sampling for ATR-101 PK assessment (trough levels)

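### The washout comparisons in SAP 6.8 and 6.9 leave out the washout that follows a response at Dose Levels 1–4, the one most needed to attribute the response to ATR-101

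*SAP*

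**What the plan says.** **Responder rule and washout comparisons.** SAP 6.8: "A responder is defined as a subject who meets the primary outcome measure of Day 15 17-OHP" no higher than 2×ULN, at any dose level. It then lists changes in 17-OHP over the washout. Four run from Day 15 of Levels 1–4 to Day 1 of Levels 2–5. The fifth is "Change and percentage change from Dose Level 5 Day 15 to" the Final Study Visit. Two further percentages follow, both in the Safety Population. A *placebo responder* is at or below 2×ULN at one of the italicised end visits in that list. A subject with a *placebo effect* is a placebo responder, or has a negative mean percentage change from Day 15 to the following level's Day 1. SAP 6.9 uses that same interval for the other steroids.

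**Purpose of the washout and path of a responder.** Protocol 3.2: "This period also serves to verify that changes in adrenal steroids and steroid intermediates are due to ATR-101 effects". Protocol 3.1.5: "The Final Study Visit will take place once a subject has met the primary outcome measure at the completion of Dose Levels 1-4", or after Level 5.

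**Sampling at the Final Study Visit.** Protocol 7.6, repeated in 7.7 for early termination: "If the morning dose of replacement steroids (GC/MC) was taken, it is acceptable to complete the Final Study Visit". Steroid sampling is among the procedures listed for that visit. Protocol 6.11 says that when the morning-dose and clock-time conditions are not met, "the blood sample for steroid hormones must not be collected; the visit procedures should not be performed".

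**Glucocorticoid (GC).** SAP 4.1 and Protocol 3.3 say that raised GC levels could lower ACTH and then 17-OHP, and so confound the assessment. Protocol 5.3.9 asks for a stable regimen, then adds: "However, changes are permitted to ensure subject safety". Protocol 6.11: "If exogenous GC levels are suspected of confounding the efficacy outcome measures, additional testing may be performed".

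**The concern.** The trial has no parallel control arm. Its evidence that a fall in 17-OHP comes from ATR-101 is within-subject: the value falls on drug and returns on placebo. For a responder, the informative washout is the one straight after the response. A rebound supports attribution, and a value that stays low weakens it. If the planned comparisons end at a visit that responders do not have, the check is made mainly in subjects who did not respond.

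The second strand is smaller. The SAP names raised GC as a possible confounder and says GC levels will be assessed for that reason, but it does not say how the measurements or regimen changes will be used when a response is interpreted.

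**Working it through.** **1. The plan's own percentages.** Protocol 9.1 and SAP 6.1: 2/9 = 22%, 7/9 = 78%, 7/17 = 41%. All three reproduce.

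**2. Washouts completed against comparisons listed.** Inputs: the escalation rule (Protocol 3.1, 3.1.5 and 7.4; SAP 5.1) and the five comparisons in SAP 6.8. A subject whose first response is at Level k completes k washouts. For k = 1 to 4 the listed comparisons cover k − 1 of them, because the last washout ends at the Final Study Visit. For k = 5 they cover all five.

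| Level of response | Washouts completed | Washouts in a listed comparison | Post-response washout listed? |
|---|---|---|---|
| 1 | 1 | 0 | No |
| 2 | 2 | 1 | No |
| 3 | 3 | 2 | No |
| 4 | 4 | 3 | No |
| 5 | 5 | 5 | Yes |

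The missing washout is always the one after the response. Conversely, if the escalation rule is followed, everyone in the Level 1–4 comparisons was above 2×ULN at that level's Day 15, that is, a non-responder at that level. A non-responder who completes the washout but does not escalate for safety reasons drops out in the same way.

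**3. Other SAP text.** The SAP 6.9 interval and the mean-change part of the *placebo effect* definition name only the following level's Day 1. Read literally, they exclude even the Level 5 Final Study Visit. The summaries by last dose level in SAP 6.2 carry results forward but add no Final Study Visit comparison.

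**4. Denominator.** The Safety Population (SAP 6.3.2) is everyone with at least one dose of ATR-101. A Level 1 responder belongs to it but has no qualifying end visit, so can count only as not showing a placebo response or effect. With m such subjects among N, neither percentage can exceed (N − m)/N. For an assumed m = 1 this is 8/9 = 88.9% at N = 9, or 16/17 = 94.1% at N = 17.

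**5. GC information, collected against analysed.** Collected: a separate GC/MC case report form (Protocol 5.3.8) and a synthetic GC screen, which Protocol Table 5 puts in its own row apart from steroid hormones and intermediates. Analysed: baseline GC and dose (SAP 6.5), concomitant-medication summaries and listings (6.6), and progesterone, cortisol and ACTH (6.9). The screen and on-study regimen change are not named, and none of these outputs is tied to a subject's responder status. The Per Protocol repeat turns on an undefined significant deviation (6.3.3), and a GC change that Protocol 5.3.9 permits need not be one.

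**6. Weight of one subject.** 1/9 = 11.1 points; 1/17 = 5.9 points.

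**The case against.** **The placebo-responder sentence may already cover it.** It names the Final Study Visit beside Day 1 and refers to any dose level, so one could take it to include a Level 1–4 responder's last visit. The wording is ambiguous. However, its closing clause limits it to the italicised visits, and the only Final Study Visit there is the one that follows Level 5. Even the wider reading leaves the change summaries and the mean-change part of *placebo effect* uncovered.

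**The table shells may handle it.** They are a separate document (SAP section 8) and were not seen. That limits what can be said about the outputs, but not about the SAP text.

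**Most responders may be at Level 5.** A reader might infer that the check misses most responders. The documents do not support that. They give no distribution of response by level, describe Level 1 as intended to be non-effective (Protocol 3.2), and expect high entry values (Protocol 3.3). Four of five is a count of dose levels, not of responders.

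**Responders are selected for a low Day 15 value.** Some rebound would appear through regression to the mean alone. This stands, and the fix must say so.

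**GC information is already available.** With 9 to 17 subjects, the medication listings can be matched to responders by hand. This largely stands, which is why the GC strand is secondary. Also, a GC level raised through CYP3A is itself an effect of ATR-101. It bears on mechanism, not on whether treatment produced the response. Only a regimen increase bears on attribution.

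**Inflated false-positive rate.** A reader might infer a measurable inflation. Take a 20% null, inferred because a minimax search for 20% against 50% returns 2/9 and 6/17. Let q be an assumed chance that a non-responder crosses the threshold through a GC increase, so that the rate becomes 0.20 + 0.80q. Under the Protocol 9.1 rule the chance of success is 3.4%, 8.2% and 15.8% at q = 0, 5% and 10%. With a 10% null it is 0.1%, 0.6% and 2.6%. Neither the null rate nor q is in the documents. The sum also assumes that the null rate excludes GC-driven responses, and it does not describe the modified Stage 1 rules in SAP 6.1. These figures are not evidence of bias.

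**Conclusion.** The washout gap holds on the text. At 4 of the 5 dose levels the washout after a response is in no listed comparison, and a Level 1 responder has none while remaining in both placebo denominators. This rests on the escalation rule being followed and on the restrictive reading of the placebo-responder sentence. It weakens the attribution check that Protocol 3.2 relies on. It does not change the primary response rate.

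The GC gap is real but descriptive. One reclassified responder is worth 11.1 points at n=9 or 5.9 points at n=17, and without a frequency of GC increases the bias cannot be sized. A reader might conclude that the responder definition is invalid because it uses 17-OHP alone. The documents do not support that, and the definition should stay.

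Protocol 7.6 and 7.7 conflict with 6.11 on whether a steroid sample may be collected after the morning GC/MC dose. The passages must be reconciled, because that sample closes the missing comparison.

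**What to change.** **Washout (SAP 6.8 and 6.9).** Define one comparison for every dose level k and every subject who completes the washout: Day 15 of level k to the next post-washout visit, which is Day 1 of level k+1, or the Final Study Visit if the subject does not escalate. Use it in the *placebo responder* and *placebo effect* definitions too. Show responders and non-responders separately. State that responders are selected for a low Day 15 value, so part of any rebound may be regression to the mean. Flag Final Study Visit samples drawn after the morning GC/MC dose, and reconcile Protocol 7.6/7.7 with 6.11.

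**GC (SAP 6.8).** Beside the unchanged primary result, add one sensitivity row. In it, a Day 15 response is not counted if the recorded GC regimen at that Day 15 was above the Dose Level 1 Day 1 regimen, or was raised, even temporarily, during that treatment period. Flag any change of compound separately. An increase made during the lead-in becomes part of that baseline and should be noted.

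**Cost.** SAP wording, a revised derivation and one table row, all from visits and data already planned. The row may undercount true responders whose GC was raised for an unrelated reason, so it should not replace the primary result. With 9 to 17 subjects, everything here is descriptive.
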